In addition the DSMB may convene additional meetings if necessary to ensure the ongoing monitoring and safety of the subjects treated with FMT. The internal DSMB will include the following individuals: [name] (Gastroenterology – BIDMC, Chair), [name] (Infectious Diseases – BIDMC), [name] (Gastroenterology – University of Pennsylvania)

All events will be reported directly to the DSMB and the Institutional Review Board (IRB) in accordance with Harvard University policy: Investigators will promptly report to the IRB all unanticipated problems involving risks to human subjects or others under Title 21 of the Code of Federal Regulations (21 CFR 312.32) part 56 (Institutional Review Boards), part 312 (Investigational New Drug Application), and part 812 (Investigational Device Exemptions). Harvard Medical School policy is consistent with guidance set forth by the Office for Human Research Protections (OHRP) (presented January 15, 2007)

<http://www.hhs.gov/ohrp/policy/AdvEvntGuid.htm> and the FDA (presented January 14, 2009) <http://www.fda.gov/downloads/RegulatoryInformation/Guidances/UCM126572.pdf> when determining what related events require review by the Institutional Review Board. Any serious AEs also will be evaluated by the DSMB for review and determination of whether the trial should continue.

All subjects will be followed for an additional six months following the end of their treatment. Subjects that did not experience a AEs or SAEs will receive a telephone call to monitor their current symptoms and quality of life. For subjects that did experience a AE or SAE that was found to be connected to the FMT treatment, we ask that they return to our medical center for an exam with their gastroenterologist. All treatment and outcome of AEs will be documented on the CRF and summarized in the CSR. All AEs will be followed to resolution or stabilization by the study physician.

9. Statistics

Power Calculations

Assuming 60% endoscopic recurrence in the control arm, and 20% in the FBT arm, the study would require 22 patients in each arm (Total N=44) to have 80% power. These assumptions are based on endoscopic recurrence data from the Reguero trial, which represents typical patient populations coming to ileo-colectomy at tertiary referral centers¹⁶. This cohort could be enrolled from 4 participating sites (N=11 per site) that perform >30 ileo-cecal resections per annum.

Statistical Analysis Plan

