For the primary end-point, chi-square test (or Fisher's exact test if any cell number <5) will be used to compare the proportion of patients in each arm who exhibit endoscopic recurrence (Rutgeerts score ≥ 12) at 6 months. A p value <0.05 will be considered significant.

For the secondary end-points, dichotomous variables will be summarized using frequency tables or proportions, and compared using chi-square or Fisher's exact test. Continuous variables will be expressed as mean values \pm standard error, and compared using unpaired, two-tailed Student's t-tests and one-way analysis of variance (ANOVA) for multiple group comparisons. Data that lack normality will be analyzed using non-parametric tests (Mann-Whitney). P-values < 0.05 will be considered significant, after correction for multiple tests. Data will be analyzed using JMP software (SAS, Cary, NC). For microbial diversity, we will apply a set of downstream statistical tests to the resulting microbial, viral, gene, pathway, and metabolite abundances. Transformed data from groups will be compared using Bray-Curtis similarity, multidimensional scaling, and analysis of similarity (ANOSIM) (Primer E, Plymouth, UK). ANOSIM will also be used to compare

intersubject and intrasubject TRFLP profile similarities. Analysis of variance (ANOVA) will be used to compare relative abundance of specific TRFLP pattern elements between each group of subjects. These tests will take into account covariates included in available or collected sample metadata (age, family history, treatment, environmental/demographic data, and diet) by leveraging our LEfSe univariate biomarker discovery method and its multivariate successor MaAsLin. Such statistical tests will provide a measure of expected reproducibility of predicted microbial biomarkers that is not attainable by unsupervised ordination methods (e.g. Principle Coordinates Analysis) as provided by other software such as QIIME.

10. Direct Access to Source Data/Documents

The investigator will permit trial-related monitoring, audits, IRB/IEC review, and regulatory inspection(s) by providing direct access to source data/documents.

11. Quality Control and Quality Assurance

Good Clinical Practice will be adhered to in screening, preparation and administration of donor stool. All research staff are trained in Responsible Conduct of Research of clinical trials.

12. Ethics

Special Ethical Considerations: None

Subject Confidentiality: as described above

Placebo Use: N/A

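### The plan says its microbiome feature tests will measure biomarker reproducibility, but no step it describes estimates it; subject-level resampling would

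*Combined protocol and SAP*

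**What the plan says.** The microbiome is a secondary endpoint (sections 4 and 7), with stool sampled at screening and at eight later time points. For its analysis, section 9 (Statistical Analysis Plan) states: "we will apply a set of downstream statistical tests to the resulting microbial, viral, gene, pathway, and metabolite abundances". It names ANOSIM on Bray-Curtis similarity, ANOVA on the relative abundance of individual profile elements, and covariate-adjusted feature testing "by leveraging our LEfSe univariate biomarker discovery method and its multivariate successor MaAsLin". The paragraph ends with the claim at issue: "Such statistical tests will provide a measure of expected reproducibility of predicted microbial biomarkers that is not attainable by unsupervised ordination methods".

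On multiplicity, the same section says of the secondary endpoints: "P-values < 0.05 will be considered significant, after correction for multiple tests". It names neither the method nor the family of tests, and does not say whether the feature-level tests are included.

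The data come from one cohort. Section 4 (Trial Design) plans 50 patients who choose their own arm; section 9 (Power Calculations) is built on 44. No second cohort, split sample, cross-validation, bootstrap or reproducibility metric is described.

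**The concern.** Reproducibility asks whether a feature found here would be found again, with a similar effect, in other patients. A p-value or effect score from the data that picked the feature does not answer that. Features pass partly because they are real and partly because chance helped them, so the effects that survive selection are on average too large. The excess depends on true effect sizes that the analyst does not know.

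Microbial diversity is one of the four outcomes listed in section 3, and the trial's hypothesis is itself about the microbiome. Section 12 calls the trial a pilot and anticipates further studies. If a feature list is published as carrying a measure of expected reproducibility, readers may give it, and its effect sizes, more weight than the analysis supports.

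**Working it through.** **1. The plan's own figure.** The documents give no number for biomarker reproducibility. The only related figure is the sample size for the primary endpoint: "Assuming 60% endoscopic recurrence in the control arm, and 20% in the FBT arm", for which "the study would require 22 patients in each arm (Total N=44) to have 80% power". With pooled variance, two-sided 0.05 and no continuity correction, and with mean proportion (0.6 + 0.2)/2 = 0.4:

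n = [1.96 × √(2 × 0.4 × 0.6) + 0.842 × √(0.6 × 0.4 + 0.2 × 0.8)]² / 0.4² = (1.358 + 0.532)² / 0.16 ≈ 22.3, rounded up to 23 per arm.

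Power at 22 per arm is 79.4%. The stated 22 is therefore reproduced to within one patient. It fixes the cohort size used below and has no other bearing on this point.

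**2. Step by step through the text.** For each named method, does its described output estimate replication?

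- ANOSIM: a group-level similarity test. No.
- ANOVA on profile elements: feature-level p-values from the full cohort. No.
- LEfSe and MaAsLin, as described: feature discovery with covariates on the full cohort. No validation step is described.
- Correction for multiple tests: limits false selections. It does not estimate replication.

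**3. Illustration of the gap.** Assumptions that are not in the documents: 22 per arm, 500 independent normal features, 50 of them (10%) truly shifted by d SD, t-tests, and Benjamini-Hochberg at 5%. Replication means p<0.05 in the same direction in a second, identical trial.

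The benchmark is that second trial's own power for a feature known to be real. This is the power of a two-sided t-test with 42 degrees of freedom and noncentrality d × √(22/2):

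- d = 0.5: noncentrality 1.66, power 37%
- d = 0.8: noncentrality 2.65, power 74%
- d = 1.2: noncentrality 3.98, power 97%

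| True d | Selected features that replicate | Power of the repeat trial | Mean estimated effect of selected features | Inflation |
|---|---|---|---|---|
| 0.5 SD | about 30–35% | 37% | about 1.35 SD | 1.35/0.5 ≈ 2.7-fold |
| 0.8 SD | about 70% | 74% | about 1.24 SD | 1.24/0.8 ≈ 1.6-fold |
| 1.2 SD | about 93% | 97% | about 1.31 SD | 1.31/1.2 ≈ 1.1-fold |

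At d = 0.5, separate runs gave mean estimates between about 1.2 and 1.4 SD. The figure is unstable because fewer than one feature per trial is selected on average (about 0.8).

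**4. Why the estimates barely move with the truth.** With 500 tests, the first Benjamini-Hochberg step needs p ≤ 0.05/500 = 0.0001. At 42 degrees of freedom that is |t| of about 4.30, or an observed difference of 4.30 × √(2/22) ≈ 1.30 SD. The bar eases as more features pass. When true effects are small, the size of a selected effect is set largely by the threshold.

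**5. What the correction does achieve.** With no true difference and 100 to 1000 features, Benjamini-Hochberg selects any feature in only 4–6% of trials. In the scenarios of step 3, about 88–95% of the selected features are real.

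**The case against.** The strongest reply is that the sentence is comparative. Ordination gives no feature-level test, and supervised tests do. That comparison is fair. Corrected tests also carry some indirect information on replication, since most features that pass are real. What stands against the plan is narrower: indirect information compatible with replication anywhere from about 30% to 93% is not a measure of it.

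Three stronger readings are tempting, and the documents do not support them.

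- *A reader might infer that the biomarkers will look far more reliable than they are.* That depends on the number of features, the true effects and the correction, none of which is stated. One can produce near-perfect apparent discrimination from noise by scoring patients on the best few of many features, but the plan proposes no such score, and that exercise ignores the stated correction.
- *A reader might take the low replication at 0.5 SD as evidence of false biomarkers.* It is mostly a small repeat trial missing real effects, because the rates sit close to that trial's own power.
- *A reader might say the plan states that it selects and assesses on the same patients.* It does not say so. This is an inference from a single cohort and the absence of any validation step. If a named tool resamples internally, the plan neither describes that nor says its output is the promised measure.

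It also stands that no stopping rule, decision rule or primary analysis uses a biomarker.

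**Conclusion.** The point holds as a gap between a claim and the methods described: section 9 promises a measure that none of its steps yields. Correction for multiple tests, if it covers the feature-level tests, keeps false selections low. It leaves effect inflation in place, which is large when true effects are modest (about 2.7-fold at 0.5 SD) and small when they are strong (about 1.1-fold at 1.2 SD). These sizes rest on assumed feature counts, independent normal features and equal arms. Real abundances are correlated and skewed, and patients choose their arm, so the figures are illustrative only. The absence of a described validation step does not depend on them. This is a minor point about a secondary analysis, and the primary endpoint comparison is unaffected.

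**What to change.** Add to the Statistical Analysis Plan:

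1. Repeated resampling by subject, by cross-validation or bootstrap. Keep all of a subject's samples together and redo both feature selection and multiplicity correction in each resample. Fix the scheme in advance, because selection frequency depends on it.
2. For each feature, report its selection frequency and its out-of-sample effect estimate.
3. Name the correction method and its family, and state that it covers the feature-level tests in all five data classes.
4. Label the list exploratory pending external replication. Internal resampling speaks only to patients like these, and it does not remove confounding from self-chosen arms.

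Do not validate by leaving out one site at a time. The site figures are a feasibility statement ("This cohort could be enrolled from 4 participating sites (N=11 per site"), and with self-chosen arms a site of about 11 patients may have few or none in one arm.

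If resampling is not done, remove the reproducibility claim. The cost is modest extra analysis code and wording, and probably a less favourable feature list. No data collection changes.
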